## 1. Purpose - in nontechnical, lay language

a. Summarize the purpose and objectives of this protocol in one short paragraph. There are over 7 million people living with stroke in the United States. Per year, approximately 17,000 veterans are admitted to the VA for acute stroke. Chronic pain after stroke can occur between 10-50% of stroke survivors. Post-stroke pain (PSP) can lead to further complications in a stroke survivor's recovery. Exercise has improved PSP and associated symptoms such as mobility, fatigue, and quality of life. Repetitive transcranial magnetic stimulation (rTMS) is a noninvasive technique using electromagnetic induction for cortical neurostimulation. The use of rTMS has been explored shown to be effective in treating chronic PSP but is limited in effect duration. Our proposal will test the hypothesis that rTMS is feasible and safe to be paired with exercise. Additionally, we believe a complementary effect can develop to enhance the neurostimulation duration of rTMS.

b. Describe how outcomes will be measured for this protocol. We will collect outcome measures as listed in Table 1: Schedule of Events below. Additionally, we will collect feasibility metrics (recruitment, refusal, attrition and retention rates) and safety outcomes. Finally, neuroimaging will be obtained and we will perform structural and functional connectivity analysis of the pre- and post-intervention imaging.

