reserve and target heart rate dosing. Thus, repetition and time spent exercising matters less but reaching a certain physiologic state demonstrates reaching a sustainable target benefit from exercise. In stroke studies involving exercise, intervention begins  $\geq 1$  month after stroke. Our target population of persistent post-stroke headaches are required to have had symptoms  $> 3$  months after their stroke. Exercise can be performed in patients with walking difficulty because of the stationary cycle, to reach target dosing.

Repetitive transcranial magnetic stimulation (rTMS) uses noninvasive electromagnetic induction for cortical neurostimulation. The use of rTMS has been explored in several trials for patients with neuropathic pain including those with chronic PSP. The primary motor cortex has been used as the primary site for stimulation in several studies, including multicenter double-blind sham-controlled randomized clinical trials, examining the efficacy of rTMS for chronic PSP. Studies suggest that neurostimulation of the motor cortex modulates interconnected neural structures modulate pain pathways. rTMS allows for mapping of the brain, specifically locating the motor cortex and stroke lesion, to deliver more targeted stimulation compared with transcranial direct current stimulation. One-month post-intervention follow-up evaluation has precedent in prior studies using rTMS to treat headaches to estimate treatment effect. The clinical trials that showed improvement in pain scores received high frequency rTMS at the motor cortex.

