rTMS was shown to be beneficial in multiple type of pain syndromes including musculoskeletal [30] and myofascial pain. A commissioned panel of European experts to establish rTMS guidelines on therapeutic use gave high frequency rTMS of the contralateral primary motor cortex a Level A recommendation for the evidence as a definite analgesic effect with few safety issues. However, the effects of the treatment are transient, usually lasting only a few hours to days. For rTMS to be a practical therapy for chronic PSP, more sustained efficacy would need to be demonstrated. In rTMS studies for stroke rehabilitation, neurostimulation was delivered prior to the physical activity. This additional neurostimulation was thought to help sustain motor recovery from the physical activity. We hypothesize that pairing rTMS prior to exercise develops a paired effect to enhance the duration of symptomatic relief in veterans suffering from chronic PSP.

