### 3. Participants (Screening and Selection)

a. How many participants are to be enrolled?

Up to 100 patients will undergo the screening process. Our goal is to enroll 32 patients. We anticipate having to randomize 36 patients to reach the anticipated 32 patients that complete the study in entirety.

b. Describe the characteristics of anticipated or planned participants (if multiple groups, repeat list for each group).

Sex: both

Race/Ethnicity: all

Age: 19-89

Health status: stroke patients with headaches

c. From what population(s) will the participants be derived? Patients with stroke and headaches presenting to the Birmingham VA hospital will be recruited.

Describe your ability to obtain access to the proposed population that will allow recruitment of the necessary number of participants: [name] is a stroke neurologist at the BVAMC and has access to all stroke patients admitted to the BVAMC.

d. Describe the inclusion/exclusion criteria:

Inclusion Criteria: 1) Male or female Veteran of US military  $\geq 19$  years of age; signed informed consent; 2) Minimum of 3-months since time of stroke and medically stable; 3) Headache has persisted for  $> 3$  months after stabilization of the stroke; 4) Ability to walk or tolerate recumbent cycle ergometry for 10 mins

without assistance; 5) Stable pain medication regimen for ≥1 month prior to study; 6) Females of child-bearing potential (i.e. not postmenopausal or surgically sterile) must be using a medically acceptable method of birth control and should not be pregnant nor have plans for pregnancy or breastfeeding during the study; 7) Completed diagnostic, maximal graded exercise test including 12-lead ECG and indirect calorimetry (i.e. oxygen uptake, minute ventilation, respiratory exchange ratio, etc.), and cleared for participation by an nurse research coordinator; 8) Minimum pain intensity of 30 on the Mechanical Visual Analogue Scale on average with pain symptoms.

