Exclusion Criteria: 1) Moderate to severe cognitive impairment (Montreal Cognitive Assessment score <16/30); 2) Pre-stroke modified Rankin >2; 3) History of seizures; 4) Presence of any standard TMS or MRI contraindications (see human subjects); 5) Current diagnosis of DSM-5-defined bipolar disorder I, schizophrenia, schizoaffective disorder, or obsessive-compulsive disorder; 6) Diagnosis of moderate or severe substance use disorder (except for caffeine and nicotine) during the preceding 3 months (Participants must agree to abstain from illicit drugs during the study); 7) Increased risk of suicide that necessitates inpatient treatment or warrants additional therapy excluded by the protocol; and/or intensity of suicidal ideation (Type 4 or Type 5) or any suicidal behavior in the past 3 months on Columbia Suicide Severity Rating Scale (C-SSRS); 8) Litigating for compensation for a psychiatric disorder. Veterans who are in the process of applying for or receiving VA service-connected disability are eligible; 9) Current enrollment in another intervention trial for pain or stroke; 10) Persons imprisoned, of minor age, diagnosed with terminal illness, or require surrogate for consent; 11) Fails baseline exercise screening activities; 12) Persistent post-stroke headaches not better accounted for by another diagnosis; 13) Is unable to reliably attend intervention sessions i.e. planning to move, transportation issues; 14) Neurological disorder pre- or post-stroke affecting subject's ability to follow study directions.

e. If participants will comprise more than one group or stratification, describe each group (e.g., treatment/intervention, placebo, controls, sham treatment) **and** provide the number of participants anticipated in each group. Up to 100 patients will undergo the screening process. Our goal is to randomize 32 patients with 16 in the sham and 16 in the active rTMS group. We anticipate having to randomize 36 patients to reach the anticipated 32 patients.

f. Indicate which, if any, of the special populations listed below will be involved in the protocol. Include the Special Populations Review Form (SPRF) if indicated.

Pregnant Women: Attach [SPRF—Pregnant Women, Fetuses, Neonates/Nonviable Neonates](#)

Fetuses: Attach [SPRF—Pregnant Women, Fetuses, Neonates/Nonviable Neonates](#)

Neonates/Nonviable Neonates: [SPRF—Pregnant Women, Fetuses, Neonates/Nonviable Neonates](#)

Prisoners: Attach [SPRF—Prisoners](#)

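### Both arms exercise, so active versus sham rTMS cannot show that exercise prolongs or complements rTMS; no persistence outcome is named and the session count contradicts itself

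*Combined protocol and SAP*

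**What the plan says.** All references are to the combined protocol and SAP.

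- **What is to be tested.** Section 1.a: "Our proposal will test the hypothesis that rTMS is feasible and safe to be paired with exercise". It then adds, as a belief: "we believe a complementary effect can develop to enhance the neurostimulation duration of rTMS".
- **The background hypothesis.** Section 2 puts forward, as a hypothesis, that "pairing rTMS prior to exercise develops a paired effect to enhance the duration of symptomatic relief". It does not say compared with what. Two nearby sentences point in different directions. On rTMS used by itself, "the effects of the treatment are transient, usually lasting only a few hours to days". On rTMS given before physical activity in stroke rehabilitation, "This additional neurostimulation was thought to help sustain motor recovery from the physical activity".
- **Arms.** Section 4.a randomizes to sham or active rTMS and gives exercise to both groups. Each rTMS or sham session falls on the same day as an exercise session and before it. Section 3.e: "Our goal is to randomize 32 patients with 16 in the sham and 16 in the active rTMS group". Section 3.a: "We anticipate having to randomize 36 patients to reach the anticipated 32 patients that complete the study in entirety".
- **Pain data.** Table 1 (Sections 4.a and 4.e) schedules the VAS, pain journal and Brief Pain Inventory at baseline, weekly in weeks 0 to 8, and at the 1-month visit. Section 4.a adds pain ratings before and after rTMS.
- **Follow-up.** Section 2: "One-month post-intervention follow-up evaluation has precedent in prior studies using rTMS to treat headaches to estimate treatment effect". It reports no result from those studies.
- **Analysis.** Section 1.b refers to the Table 1 list, feasibility metrics and safety outcomes. The only analysis it names is of imaging connectivity.
- **Sessions.** Section 4.a gives three sessions a week for 8 weeks, and in the exercise paragraph a total of 10. Section 4.h ties payments to visits 5 and 10 and to a 30-day follow-up.

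**The concern.** The rationale in Sections 1 and 2 is that rTMS relief is short and that pairing it with exercise may make it last. To show that, some patients would have to receive rTMS without exercise, and none do. If active and sham differ at 1 month, it would be natural to set that against the short duration quoted for rTMS and credit the pairing. But that short duration is a historical benchmark from other studies, not a concurrent group. A course of repeated rTMS sessions could produce the same 1-month difference with no help from exercise.

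A second gap applies whichever way Section 2 is read. Duration is the target, yet the plan does not say which pain measurement, at what time and compared how, would show that relief lasted. The conflict over the number of sessions adds to this, because it leaves unclear when treatment ends and so how long after treatment the 1-month visit falls.

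**Working it through.** **1. What the two arms identify.** Let T = 1 for active rTMS and 0 for sham or none, and E = 1 for exercise. Write the mean of any pain or duration outcome as

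m(T, E) = b0 + bT·T + bE·E + bTE·T·E.

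The randomized cells are:
- active + exercise: b0 + bT + bE + bTE
- sham + exercise: b0 + bE

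Active minus sham = bT + bTE, that is, the effect of rTMS alone plus any interaction with exercise, not separated.

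The pairing statement needs either bTE (complementarity) or bE + bTE (paired treatment minus rTMS alone). Take any weighted sum of the two cells, with weights a and c. The coefficients are a + c on b0, a on bT, a + c on bE, and a on bTE.
- For bTE alone, the coefficient on bT must be 0 and that on bTE must be 1. Both equal a, so this is impossible.
- For bE + bTE, the coefficient on b0 must be 0 and that on bE must be 1. Both equal a + c, so this is impossible.

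Sample size does not enter. The design has rank 2 against four parameters.

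**2. The two readings of Section 2.**
- Exercise prolongs the relief from rTMS: needs rTMS without exercise; not testable here.
- rTMS prolongs the benefit of exercise: needs exercise with sham; that is the control arm, so this is testable.

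**3. Precision.** The documents give no SD, effect size, alpha or power, so the sample size cannot be reproduced. Results are in SD of a single pain score, two-sided 95%, equal variances, unadjusted for baseline. All rows are on this one scale.

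| Design | SE (in SD) | t | Half-width |
|---|---|---|---|
| Two arms, 16 each | √(2/16) = 0.354 | t(30) = 2.042 | 0.72 |
| Two arms, 18 each (all 36) | √(2/18) = 0.333 | t(34) = 2.032 | 0.68 |
| Three arms, 32 in all, paired minus rTMS alone | √(2/10.67) = 0.433 | t(29) = 2.045 | 0.89 |
| 2×2, 8 per cell, interaction | √(4/8) = 0.707 | t(28) = 2.048 | 1.45 |

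A third arm (rTMS without exercise) makes bE + bTE estimable but still not bTE. The interaction needs the fourth cell as well.

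**4. Session count.** 3 per week × 8 weeks = 24, against the stated 10. Ten sessions at 3 per week take 10/3 = 3.3 weeks; ten sessions over 8 weeks are 10/8 = 1.25 per week. The three figures cannot all hold.

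Assume sessions on days 0, 2 and 4 of each week. The 10th then falls on day 21 and the 24th on day 53. A visit 30 days after week 8 is on day 56 + 30 = 86, which is 86 − 53 = 33 or 86 − 21 = 65 days after the last session. Counted from the last session it would be 30 days in either case. The 65-day figure is an outer bound: it has treatment stopping after about three weeks, which the repeated 8-week statements speak against.

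**The case against.** The strongest defence is that Section 1.a separates what the proposal will test from what the investigators believe, and that a small feasibility trial need not test a mechanism. That stands. A reader might infer that the trial cannot test its own hypothesis; the documents do not support this, because the hypothesis stated for testing is feasibility and safety, and two arms can address it. The defence does not cover Section 2, which states longer relief as a hypothesis and leaves open a reading the design cannot address.

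Three further inferences also go too far.
- *That pain after treatment is not measured, or that follow-up is undefined.* Table 1 schedules the VAS, journal and Brief Pain Inventory at the 1-month visit, and Section 2 describes that visit as following the intervention. What is missing is a named outcome and contrast, plus an unambiguous last session.
- *That the payments at visits 5 and 10 confirm ten sessions.* Section 4.h speaks of visits. If baseline is week 0, screening plus weeks 0 to 8 is 1 + 9 = 10 visits, so the payment text settles nothing.
- *That the trial needs more arms.* On a common scale, a third arm or a 2×2 would answer a pairing question only with wide intervals at 32 patients.

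It is also fair to say that a daily diary with a week-by-week model would be a preference and a burden, not a requirement.

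**Conclusion.** The point holds in a limited form. The trial can address feasibility and safety, and it can estimate active versus sham rTMS in patients who all exercise. It cannot show that exercise prolongs or complements rTMS, and a 1-month arm difference could not be attributed to pairing. This part follows from the allocation alone and needs no numerical assumption.

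No persistence outcome or between-arm pain contrast is named, although the data for one are already scheduled. Where one is named, an unadjusted single-score comparison would have a half-width of about 0.72 SD at 16 per arm, or 0.68 SD if all 36 are measured and split evenly. Those figures assume equal variances and approximate normality; baseline adjustment should narrow them by an amount the documents do not let us calculate.

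The 24 versus 10 sessions is a plain contradiction. The day counts shown for it rest on assumed session weekdays.

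This should be corrected before results are interpreted. It does not undermine the feasibility and safety aim.

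**What to change.** 1. **Sections 1.a and 2.** Keep the feasibility and safety hypothesis. Restate the efficacy hypothesis as active versus sham rTMS added to exercise. Say explicitly that the design does not test whether exercise prolongs or complements rTMS.
2. **Sections 4.a and 4.h.** Reconcile the weekly frequency, the 8-week period and the total number of sessions. Clarify what visits 5 and 10 refer to. State whether the 1-month visit counts from the last session or from week 8, whichever is intended. This review takes no position on which schedule is right.
3. **Section 1.b.** Choose one of the pain measures already in Table 1 and name, as the measure of persistence, its baseline-adjusted between-arm difference at the 1-month visit, with a 95% confidence interval, in all randomized participants, including those who stop sessions early. Journal entries between the last session and that visit are optional.

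The cost is a more modest claim, some protocol wording and a little analysis work, plus effort to see early stoppers at 1 month. No arm, scheduled visit or patient is added.

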## 2. Background - in nontechnical, lay language

Summarize in 2-3 paragraphs past experimental and/or clinical findings leading to the design of this protocol. Include any relevant past or current research by the PI. For drug and device studies, summarize the previous results (i.e., Phase I/II or III studies).

Chronic pain after stroke can occur between 10-50% of stroke survivors. Post-stroke pain (PSP) can lead to further complications in a stroke survivor's recovery including worsening depression, causing cognitive dysfunction, and even increasing suicidality rates. PSP is caused by the stroke itself and produces moderate or severe pain. It can manifest as new onset or worsening of prior headaches and/or somatic pain in the topographic region of the brain affected by the stroke. In 2018, persistent post-stroke headache, the pain syndrome focused in this proposal, was defined in the International Classification of Headache Disorders, 3rd ed. While acute headaches after stroke resolve within 3 months, persistent post-stroke headache have been defined to last >3 months and no other pain diagnosis better explains the symptoms. While the mechanisms are poorly understood, persistent post-stroke headaches are more frequent and more severe than acute stroke-related headaches.

In stroke survivors, exercise has improved symptoms such as mobility, fatigue, and quality of life. Exercise has the added benefit of promoting social interactions that can be associated with improved self-management. A recent clinical trial of stroke patients during inpatient rehabilitation who received aerobic exercise in combination with traditional physiotherapy had significantly less pain scores than those receiving traditional physiotherapy alone. A statement by the American Heart/Stroke Association recommended that exercise should be incorporated into the management of stroke survivors, noting the evidence strongly support the benefits early after stroke. In stroke patients, optimal exercise programs have begun at least a month after stroke and durations have ranged anywhere from frequency of 3-5x a week that last 1-3 months. With exercise protocols, the goal is target-based dosing using target heart rate

reserve and target heart rate dosing. Thus, repetition and time spent exercising matters less but reaching a certain physiologic state demonstrates reaching a sustainable target benefit from exercise. In stroke studies involving exercise, intervention begins  $\geq 1$  month after stroke. Our target population of persistent post-stroke headaches are required to have had symptoms  $> 3$  months after their stroke. Exercise can be performed in patients with walking difficulty because of the stationary cycle, to reach target dosing.

Repetitive transcranial magnetic stimulation (rTMS) uses noninvasive electromagnetic induction for cortical neurostimulation. The use of rTMS has been explored in several trials for patients with neuropathic pain including those with chronic PSP. The primary motor cortex has been used as the primary site for stimulation in several studies, including multicenter double-blind sham-controlled randomized clinical trials, examining the efficacy of rTMS for chronic PSP. Studies suggest that neurostimulation of the motor cortex modulates interconnected neural structures modulate pain pathways. rTMS allows for mapping of the brain, specifically locating the motor cortex and stroke lesion, to deliver more targeted stimulation compared with transcranial direct current stimulation. One-month post-intervention follow-up evaluation has precedent in prior studies using rTMS to treat headaches to estimate treatment effect. The clinical trials that showed improvement in pain scores received high frequency rTMS at the motor cortex.

rTMS was shown to be beneficial in multiple type of pain syndromes including musculoskeletal [30] and myofascial pain. A commissioned panel of European experts to establish rTMS guidelines on therapeutic use gave high frequency rTMS of the contralateral primary motor cortex a Level A recommendation for the evidence as a definite analgesic effect with few safety issues. However, the effects of the treatment are transient, usually lasting only a few hours to days. For rTMS to be a practical therapy for chronic PSP, more sustained efficacy would need to be demonstrated. In rTMS studies for stroke rehabilitation, neurostimulation was delivered prior to the physical activity. This additional neurostimulation was thought to help sustain motor recovery from the physical activity. We hypothesize that pairing rTMS prior to exercise develops a paired effect to enhance the duration of symptomatic relief in veterans suffering from chronic PSP.

### 3. Participants (Screening and Selection)

a. How many participants are to be enrolled?

Up to 100 patients will undergo the screening process. Our goal is to enroll 32 patients. We anticipate having to randomize 36 patients to reach the anticipated 32 patients that complete the study in entirety.

b. Describe the characteristics of anticipated or planned participants (if multiple groups, repeat list for each group).

Sex: both

Race/Ethnicity: all

Age: 19-89

Health status: stroke patients with headaches

c. From what population(s) will the participants be derived? Patients with stroke and headaches presenting to the Birmingham VA hospital will be recruited.

Describe your ability to obtain access to the proposed population that will allow recruitment of the necessary number of participants: [name] is a stroke neurologist at the BVAMC and has access to all stroke patients admitted to the BVAMC.

d. Describe the inclusion/exclusion criteria:

Inclusion Criteria: 1) Male or female Veteran of US military  $\geq 19$  years of age; signed informed consent; 2) Minimum of 3-months since time of stroke and medically stable; 3) Headache has persisted for  $> 3$  months after stabilization of the stroke; 4) Ability to walk or tolerate recumbent cycle ergometry for 10 mins

without assistance; 5) Stable pain medication regimen for ≥1 month prior to study; 6) Females of child-bearing potential (i.e. not postmenopausal or surgically sterile) must be using a medically acceptable method of birth control and should not be pregnant nor have plans for pregnancy or breastfeeding during the study; 7) Completed diagnostic, maximal graded exercise test including 12-lead ECG and indirect calorimetry (i.e. oxygen uptake, minute ventilation, respiratory exchange ratio, etc.), and cleared for participation by an nurse research coordinator; 8) Minimum pain intensity of 30 on the Mechanical Visual Analogue Scale on average with pain symptoms.

Exclusion Criteria: 1) Moderate to severe cognitive impairment (Montreal Cognitive Assessment score <16/30); 2) Pre-stroke modified Rankin >2; 3) History of seizures; 4) Presence of any standard TMS or MRI contraindications (see human subjects); 5) Current diagnosis of DSM-5-defined bipolar disorder I, schizophrenia, schizoaffective disorder, or obsessive-compulsive disorder; 6) Diagnosis of moderate or severe substance use disorder (except for caffeine and nicotine) during the preceding 3 months (Participants must agree to abstain from illicit drugs during the study); 7) Increased risk of suicide that necessitates inpatient treatment or warrants additional therapy excluded by the protocol; and/or intensity of suicidal ideation (Type 4 or Type 5) or any suicidal behavior in the past 3 months on Columbia Suicide Severity Rating Scale (C-SSRS); 8) Litigating for compensation for a psychiatric disorder. Veterans who are in the process of applying for or receiving VA service-connected disability are eligible; 9) Current enrollment in another intervention trial for pain or stroke; 10) Persons imprisoned, of minor age, diagnosed with terminal illness, or require surrogate for consent; 11) Fails baseline exercise screening activities; 12) Persistent post-stroke headaches not better accounted for by another diagnosis; 13) Is unable to reliably attend intervention sessions i.e. planning to move, transportation issues; 14) Neurological disorder pre- or post-stroke affecting subject's ability to follow study directions.

e. If participants will comprise more than one group or stratification, describe each group (e.g., treatment/intervention, placebo, controls, sham treatment) **and** provide the number of participants anticipated in each group. Up to 100 patients will undergo the screening process. Our goal is to randomize 32 patients with 16 in the sham and 16 in the active rTMS group. We anticipate having to randomize 36 patients to reach the anticipated 32 patients.

f. Indicate which, if any, of the special populations listed below will be involved in the protocol. Include the Special Populations Review Form (SPRF) if indicated.

Pregnant Women: Attach [SPRF—Pregnant Women, Fetuses, Neonates/Nonviable Neonates](#)

Fetuses: Attach [SPRF—Pregnant Women, Fetuses, Neonates/Nonviable Neonates](#)

Neonates/Nonviable Neonates: [SPRF—Pregnant Women, Fetuses, Neonates/Nonviable Neonates](#)

Prisoners: Attach [SPRF—Prisoners](#)

Minors (<18 years old): Attach [SPRF—Minors](#)

Employees or students at institution where research conducted

Persons who are temporarily decisionally impaired

Persons who are permanently decisionally impaired

Non-English Speakers

**For each box checked**, describe why the group is included **and** the additional protections provided to protect the rights and welfare of these participants who are vulnerable to coercion: NA

g. List any persons other than those directly involved in the protocol who will be at risk. If none, enter "None": none

h. Describe the recruitment process (e.g., medical record review, referrals, letter of invitation, existing patients) that will be used to seek potential participants (e.g., individuals, records, specimens). Research recruitment by non-treating physicians/staff may require completion of [Partial Waiver of Authorization for Recruitment/Screening](#). **Recruitment: Veterans with chronic PSP will be recruited at the BVAMC through the inpatient neurology service, stroke clinic, pain clinic, and self-referral from clinic. The patients that are deemed eligible will have a recruitment letter mailed to them for further discussion of the study by the**

study team. After 7 days from mailing the study letter, the study team will call and/or email potential candidate from the contact information listed on their health records to confirm if they received the study letter. Recruitment prospects are high, as the Birmingham region encompasses one of the largest catchment areas for stroke in Veterans in the United States. [name] is a neurologist at the BVAMC and has direct access to the study population through the inpatient neurology service and outpatient neurology clinic.

i. If you will use recruitment materials (e.g., advertisements, flyers, letters) to reach potential participants, attach a copy of each item. If not, identify the source (e.g., IRB Protocol Number for approved databases) from which you will recruit participants. None at this time.

j. Describe the screening process/procedures for potential participants.

**Screening:** The screening procedure includes informed consent, vital signs, demographics, medication history, neurologic and psychiatric diagnostic evaluation, imaging studies, and medical history. Participants return for the baseline visit (within 2 to 30 days of screening). All potential participants will need to pass an Exercise Tolerance Test before randomization at the baseline visit. The test includes maximal graded exercise test including 12-lead ECG and indirect calorimetry (i.e. oxygen uptake, minute ventilation, respiratory exchange ratio, etc.), and clearance for participation by an Certified Registered Nurse Research Coordinator using established Exercise Clearance criteria followed the UAB Exercise Center.

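### Exclusion criterion 12 is inverted: as written it excludes the trial's own target population

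*Combined protocol and SAP*

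**What the plan says.** Section 2 (Background) identifies the condition under study as "persistent post-stroke headache, the pain syndrome focused in this proposal". It defines the syndrome by two features: duration beyond 3 months, and that "no other pain diagnosis better explains the symptoms". Later in the same section the protocol repeats who the trial is for: "Our target population of persistent post-stroke headaches are required to have had symptoms" for more than 3 months after the stroke.

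Section 3, item d, sets the eligibility rules. On the inclusion side, item 3 ("3) Headache has persisted for" more than 3 months once the stroke has stabilised) is the criterion that describes the headache itself, and item 8 adds a minimum pain intensity. Neither mentions the cause of the headache. The exclusion list opens with "Exclusion Criteria: 1) Moderate to severe cognitive impairment" and runs to item 14. Item 12 of that list reads "12) Persistent post-stroke headaches not better accounted for by another diagnosis".

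The participant summary in Section 3, item b, is broader still: "Health status: stroke patients with headaches".

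**The concern.** An exclusion list works in one direction: a person who meets an item cannot enter. Item 12 describes, almost word for word, the condition that the Background says the trial exists to study. Applied as written, it turns away the target patients and leaves only people whose headache has another explanation.

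Three things are at stake.

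- **The population.** Eligibility determines whom the results describe. A trial that followed item 12 literally could say nothing about persistent post-stroke headache.
- **Compliance.** If screening staff silently reverse the item, each target patient enrolled meets a written exclusion criterion, so each enrolment is a protocol deviation on paper.
- **Feasibility outcomes.** Section 1, item b, lists recruitment and refusal rates among the feasibility metrics. Such rates depend on who counts as eligible. If the criterion is applied literally, or differently by different staff, the screening log no longer gives a clear denominator.

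**Working it through.** The protocol gives no figure to reproduce here. The check is logical and uses only the protocol's text.

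**Inputs**

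- Definition of the syndrome and statement of the target population: Section 2.
- Headache duration criterion: Section 3, item d, inclusion item 3.
- Criterion in question: Section 3, item d, exclusion item 12.
- Planned numbers: Section 3, items a and e (36 randomised so that 32 complete).

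**Step 1: notation.** Let P mean headache persisting more than 3 months after stroke, and D mean that another diagnosis explains the headache better.

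- Target population (Section 2): P and not-D.
- Inclusion item 3 requires: P.
- Exclusion item 12 removes: P and not-D.

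**Step 2: apply the rules to each type of patient.**

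| Patient | In the target population? | Passes inclusion item 3? | Removed by exclusion item 12? | Can enter as written? |
|---|---|---|---|---|
| P and not-D | Yes | Yes | Yes | No |
| P and D | No | Yes | No | Yes, if other criteria are met |
| not-P | No | No | Not applicable | No |

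The target set and the set removed by item 12 are identical, so the target patients left eligible form an empty set. Those who remain are P and D, which falls outside the Background's definition.

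**Step 3: look for text that corrects it.**

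- Inclusion item 3 concerns duration only.
- Exclusion item 14 concerns neurological disorders that impair following study directions. It does not concern the cause of the headache.
- Section 3, item h, says that Veterans with chronic post-stroke pain will be recruited and from which services. It describes recruitment sources and sets no eligibility rule.
- Section 3, item j, includes a neurologic and psychiatric diagnostic evaluation at screening, but gives no rule for what its result means for eligibility.

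Item 12 is therefore the only criterion that deals with the no-better-diagnosis half of the definition, and it points the wrong way.

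**Step 4: is it an artefact of the text?** Item 12 is complete, numbered, and sits in sequence between items 11 and 13. It has no gap or redaction, and nothing marks it as superseded.

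**Step 5: size under the literal reading.** Target patients eligible: 0 of the 36 to be randomised, and so 0 of the 32 expected to complete. Everyone who could be enrolled (100%) would have a headache better explained by another diagnosis.

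**The case against.** The best defence is that the intent is unmistakable. The Background names and defines the syndrome, Section 3 describes stroke patients with headache, and the recruitment text speaks of chronic post-stroke pain. A literal reading of item 12 defeats all of this, so no sensible screener would adopt it. On this view the item is a drafting slip, either a stray negative or an inclusion criterion placed in the wrong list, and its real effect is a mismatch between screening records and the written rule. The figures of 0 and 100% then restate a reading nobody will use. The diagnostic evaluation at screening also gives staff a way to detect other causes of headache.

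Much of this is fair. Staff will probably infer the intent, and the figures describe the literal text; they do not forecast conduct. The effect on recruitment and refusal rates is conditional too: if everyone reverses the item in the same way, the eligible pool is the intended one, and the protocol does not define the denominators in any case.

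The core is untouched. Eligibility criteria are applied and audited as written. Guessing the intent correctly still leaves every target enrolment in breach of a written exclusion. Ignoring the item instead leaves no criterion on the cause of the headache, since a diagnostic evaluation without a decision rule is not an eligibility criterion. That the slip is easy to recognise makes it easy to correct, but does not make the written rule usable.

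**Conclusion.** The concern holds. Exclusion item 12 contradicts the definition of the study population in Section 2, and nothing else in the protocol resolves the conflict. It is an internal contradiction in a rule that decides who enters the trial, and it must be fixed.

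The stated size rests on one assumption, that the item is applied as written. If staff consistently reverse it, the enrolled population may be the intended one. The cost is then a recordable deviation for each target patient, potentially all 36 randomised, with no enforceable rule against headaches of other origin. The conclusion does not depend on any sample-size, effect-size or error-rate assumption. The documents do not show how the error arose.

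**What to change.** Make one of two changes to Section 3, item d:

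1. Reword exclusion item 12 along these lines: *Headache better accounted for by a diagnosis other than persistent post-stroke headache.*
2. Delete item 12 from the exclusion list and add its requirement to inclusion item 3, so that item 3 demands both the duration and the absence of a better-fitting diagnosis.

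Both give the same eligible population and agree with Section 2. Merely striking the word *not* from item 12 is less clean: under the Background's definition, a persistent post-stroke headache has no better explanation, so the shortened item would describe nobody.

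The cost is a one-line protocol amendment, with the same change carried into any screening checklist that repeats the item. No patients, visits or procedures are added. If screening has already begun, record how item 12 has been applied so far, so that the screening log and the feasibility rates can be interpreted.
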